**Study Title**

Radio-frequency rejuvenation for pelvic floor and vagina

**Protocol No**

**Sponsor** InMode MD Ltd.

**Investigational Product** The Votiva system has been cleared by the United States Food and Drug Administration (FDA) for sexual dysfunction and pelvic floor relaxation.

**Study Design** Prospective clinical study.

**Study Objectives****Primary Objective:**

Evaluate the effects of radiofrequency on pelvic floor strength as measured by intentional muscle contraction.

**Secondary Objective:**

- Evaluate the effects on subjective symptoms associated with pelvic floor weakness, including urinary symptoms, sexual function, sensitivity to climax, colorectal-anal symptoms
- Evaluate patients' subjective efficacy and change of quality of life treatment.
- Evaluate patients' satisfaction at follow up visit

**Primary Endpoints**

- Completion of all proposed visits.
- Voluntary withdrawal of the patient at any time.

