**Objective measurements:**

- Genitalia(vaginal and labia) condition and intentional muscle contraction will be evaluated at baseline, before each treatment and at follow up visits (8 weeks after each treatment). Visits 2, 4 and 6.

- Physical measurements of vagina, vulvar and perineal areas will be measured according to POP-Q guidelines. (Appendix 11.0) Visits 2, 4 and 6.

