**Study Duration**

Study duration for each subject is approximately four months (including screening, 2 treatment sessions 8 weeks apart and a follow-up visit at 8 weeks post last treatment.

Overall study duration will be approximately 12 months, depending on the subject recruitment rate.

Each subject will undergo 7 study visits including screening, 2 treatment and 1 follow-up visit.

**Visit 1:** Midwest Plastic Surgery-Evaluation

- Screening will be performed to determine subject eligibility as well as to collect all of the required medical information and obtain signed Informed Consent.
- Baseline photographs of the treatment area will be taken
- Pre-procedure questionnaires will be completed at this time
- Time required 1.5 hours

**Visit 2:** Antares Institute-Evaluation

- A complete pelvic floor assessment will be performed including but not limited to the following: measurement of internal and external pelvic floor contraction, measurement of vaginal canal length and diameter, measurement of the introitus, and length of the labia majora and minora. Measurements will be obtained following POP-Q protocol
- This visit will confirm inclusion criteria based on measurements.
- Time required: 1.5hrs

**Visit 3:** Midwest Plastic Surgery – 1st treatment

- Internal and external FormaV treatment
- Photographs of the treatment area will be taken after the procedure.
- Time required: 45 minutes

**Visit 4:** Antares Institute Follow-up visit – 8 weeks following first treatment

- A complete pelvic floor assessment will be performed including but not limited to the following: measurement of internal and external pelvic floor contraction, measurement of vaginal canal length and diameter, measurement of the introitus, and length of the labia majora and minora. Measurements will be obtained following POP-Q protocol.
- Time required: 15 minutes

**Visit 5:** Midwest Plastic Surgery – 2nd treatment

- Photographs of the treatment area will be taken before and after the procedure.
- Questionnaires will be completed.
- Time required: 45 minutes

**Visit 6:** Antares Institute Follow-up visit – 8 weeks following second treatment

- A complete pelvic floor assessment will be performed including but not limited to the following: measurement of internal and external pelvic floor contraction, measurement of vaginal canal

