#### **Main Eligibility**

#### **Criteria**

#### Inclusion Criteria

- Adult females between the ages of 35-75, seeking treatments for pelvic floor relaxation syndrome or atrophic vaginitis, which include but are not limited to: pelvic floor laxity, decreased muscle contraction in the pelvic floor, urinary incontinence, sexual dysfunction.
- Participants must have an evaluation by the Pelvic Floor Physical Therapists at Antares Institute. All participants must have a minimum of 30% below average reading on initial assessment of internal or external pelvic floor contraction in order to be included in the study.
- Negative PAP smear and pelvic exam done within last 1 year.
- The patients should understand the information provided about the investigative nature of the treatment, possible benefits and side effects, and sign the Informed Consent Form, (including the permission to use photography).
- The patients should be willing to comply with the study procedure and schedule, including the follow up visit, and will refrain from using any other treatment methods in the treatment areas such surgeries, CO2 treatment, other radiofrequency treatments and fillers injections for the last 12 months and during the entire study period.
- [name] will be available for consultation as needed throughout the course of the study. He will also review all documentation as needed.

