Cover Letter:

All enclosed below documents are part of the clinical trial NCT03536819

Study Name: Radio-frequency rejuvenation for pelvic floor and vagina

Protocol No.: DO607404A

Document date: September 20, 2017

SPONSOR: InMode Ltd.

[name]

[name]

[name]

[name]

[contact]

[contact]

I. Data analysis.

A. Analysis Sets

1. Safety Analysis Set

a) The safety analysis set will include all subjects using Votiva procedures at least a single time.

2. Performance Analysis Set

a) Performance analysis set will consist of all subjects providing at least one post treatment performance measurement.

3. Treatment of Missing Values

a) Only observed data will be used; i.e. missing data will not be imputed.

B. Statistical Analysis

1. Means, and standard deviations for each characteristic will be calculated. Paired sample t-test will be computed to assess changes in before treatment and follow-up scores. Statistical significance will be calculated and two-tail significance level of 0.05 will be used. All analyses will be conducted using IBM SPSS 21.0.

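### The listed primary endpoints are visit completion and withdrawal; no contraction reading or visit is named as primary, although contraction is the primary objective

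*Protocol*

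**What the plan says.** The primary objective (Protocol, Study Objectives) is to "Evaluate the effects of radiofrequency on pelvic floor strength as measured by intentional muscle contraction". The Primary Endpoints section has two items only: "Completion of all proposed visits" and "Voluntary withdrawal of the patient at any time".

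Contraction appears under Efficacy Endpoints instead. Objective measurements says that "intentional muscle contraction will be evaluated at baseline, before each treatment and at follow up visits (8 weeks after each treatment"), and gives Visits 2, 4 and 6. Study Duration describes each of those visits as including "measurement of internal and external pelvic floor contraction", so there are two readings per visit. Eligibility can rest on either of them: "All participants must have a minimum of 30% below average reading on initial assessment of internal or external pelvic floor contraction".

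SAP I.B.1 gives one inferential method: "Paired sample t-test will be computed to assess changes in before treatment and follow-up scores", at a two-tailed level of 0.05. It names no variable, reading or follow-up visit, ranks no outcome as primary, and gives no multiplicity rule. SAP I.A.3 adds: "Only observed data will be used; i.e. missing data will not be imputed".

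**The concern.** The listed primary endpoints do not answer the primary objective. Finishing the visits and withdrawing are disposition events. They may be definitions of the end of participation that were placed under the wrong heading, but even on that reading no contraction endpoint stands in their place.

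The study can still produce a contraction result, because Visit 2 supplies a baseline, Visits 4 and 6 supply follow-up values, and the planned test suits them. What is missing is a statement, made in advance, of which result is the primary one. Without it, any of several before/after comparisons could be presented as primary at 0.05, and a reader could not tell a planned result from a selected one. This is a single-group study of at least 20 women, so its main claim rests on that one comparison.

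**Working it through.** **1. Is a primary contraction endpoint designated anywhere?**

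- Study Objectives names the variable (contraction), but no reading and no visit.
- Primary Endpoints names completion and withdrawal only.
- Efficacy Endpoints describes a general comparison with baseline across all measurements and questionnaires.
- Objective measurements lists contraction beside genital condition and POP-Q measurements, without ranking them.
- Study Duration has internal and external contraction readings at Visits 2, 4 and 6.
- Inclusion Criteria accepts a low value on either reading, so eligibility does not point to one of them.
- SAP I.B.1 refers to pre-treatment and follow-up scores in general.

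No designation is made.

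**2. How many candidate tests are there?** With Visit 2 as baseline: 2 readings × 2 follow-ups (Visits 4 and 6) = 4.

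**3. False-positive chance if the best test is picked afterwards and nothing truly changes.**

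For independent tests:
- four candidates: 1 − 0.95⁴ = 0.1855, or 18.5%
- two candidates (Visit 6, either reading): 1 − 0.95² = 0.0975

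Independence is an upper reference, since the Visit 4 and Visit 6 changes share the Visit 2 value. The documents give no correlations, so a range was simulated: n = 20, four multivariate-normal changes with mean 0, a two-sided paired t-test on each at 0.05, and 1,000,000 trials per setting. The correlation across both reading and visit was taken as the product of the two. The Monte Carlo standard error is about 0.04 percentage points or less.

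| Assumed correlation, between readings / between visits | Any of four significant | Visit 6 only, either reading |
|---|---|---|
| 0 / 0.5 | 17.4% | 9.7% |
| 0.3 / 0.5 | 17.1% | 9.5% |
| 0.5 / 0.5 | 16.4% | 9.2% |
| 0.7 / 0.7 | 14.0% | 8.5% |
| 0.8 / 0.8 | 12.3% | 7.9% |
| 0.9 / 0.9 | 10.0% | 7.1% |

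Relative to 5%, the four-test column runs from 17.4/5 = 3.5 times to 10.0/5 = 2.0 times. Fixing the visit alone leaves 9.7/5 = 1.9 to 7.1/5 = 1.4 times, so the reading has to be settled as well.

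**4. Power of the two possible repairs.** The protocol gives no effect size, standard deviation or power, so its sample size cannot be reproduced. Taking 80% power as an assumption, the noncentral t distribution gives the detectable mean change in SDs of the paired differences:

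- One named test at 0.05: 0.66 SD with 20 pairs, 0.70 with 18, 0.75 with 16.
- Holm's first step for two readings, 0.05/2 = 0.025: 0.74 SD with 20 pairs. A 0.66 SD change then has 69.7% power.

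**The case against.** The strongest reply is that the primary variable is not missing. The objective names contraction, the visits are scheduled, the comparator is baseline, and the SAP gives the test. This is correct, and it narrows the point to the endpoint label, the reading and the visit. It does not supply any of those three.

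The visit may also be less open than four tests suggest. Study Duration counts a single follow-up visit and places it 8 weeks after the last treatment, which favours Visit 6. But the same section and Objective measurements also treat Visit 4 as a follow-up, so the text does not settle it. If Visit 6 is accepted, the right-hand column of the table applies and the inflation is smaller, though not removed.

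The error rates are conditional. They require selecting the best result after seeing the data, and the correlations are assumed. That stands, and the figures should be read only in that way.

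A further objection is that the null of zero mean change does not match the design. Visit 2 is both the reading used to confirm eligibility and the baseline, so regression to the mean can produce apparent improvement without any effect. Under assumed inputs (n = 20, reference average 100, SD 30, candidate mean 60 to 100, reliability 0.7 to 0.9, correlation 0.5 between the true internal and external values, entry if either reading is 70 or below), a single pre-named test was significant in about 5% to 21% of trials. This also stands. It is a separate bias, which naming the endpoint does not cure.

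Finally, the study has no stated success criterion, and the protocol text reads as a synopsis that cites appendices not included with it. The conclusion therefore applies to the documents as supplied. The Primary Endpoints section and the SAP's analysis text are both present, and neither makes the designation.

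**Conclusion.** The concern holds. The endpoints labelled primary cannot measure the primary objective or enter the planned test, and no contraction reading or visit is designated in their place. This should be corrected before analysis.

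The size depends on how the gap is used. With one pre-named test there is no inflation from selection. With the best of four chosen afterwards, the false-positive chance is about 10% to 17% under the assumed correlations (18.5% if independent), against the stated 5%. With Visit 6 taken as fixed and only the reading left open, it is about 7% to 10%. These figures assume 20 evaluable women, normal changes and no true change. They exclude regression to the mean and imply nothing about the sponsor's intentions.

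**What to change.** In the protocol's Primary Endpoints section, replace the two items with: *Primary endpoint: change in intentional pelvic floor contraction from Visit 2 to Visit 6 (8 weeks after the second treatment).* Before analysis, the sponsor then does one of the following:

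1. Names one reading, internal or external, as primary and the other as secondary. The reason given should take account of women being admitted on either reading.
2. Makes both readings co-primary under Holm, at overall two-sided 0.05.

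State the same choice in SAP I.B.1. Label Visit 4 contraction and all other measures as secondary, and report completion and withdrawal as subject disposition. Other pre-specified choices, such as one composite of the two readings, could also work; what matters is that one is fixed in advance.

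The cost is wording only, since the measurements are already scheduled. The drawbacks are:

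- The sponsor gives up choosing among comparisons later.
- Under option 1, the named reading may change less in women who qualified on the other one.
- Under option 2, if only one reading changes, power falls from 80% to about 70% for a 0.66 SD change with 20 pairs. The loss is smaller if both change.
- Women with a Visit 4 but no Visit 6 reading leave the primary comparison, because the SAP does not impute.

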**Efficacy Endpoints**

Comparison of measurements and patient reporting via validated questionnaires after treatments to baseline, will quantify the effects of Forma V on pelvic floor laxity and the associated symptoms.

**Objective measurements:**

- Genitalia(vaginal and labia) condition and intentional muscle contraction will be evaluated at baseline, before each treatment and at follow up visits (8 weeks after each treatment). Visits 2, 4 and 6.

- Physical measurements of vagina, vulvar and perineal areas will be measured according to POP-Q guidelines. (Appendix 11.0) Visits 2, 4 and 6.

**Subjective measurements:**

- - Subjective assessment of efficacy on sexual dysfunction symptoms, using the Female Sexual Function Index (FSFI) and Pelvic Organ Prolapse/Urinary

Incontinence Sexual Function Questionnaire (PISQ-12) questionnaire (Appendix 6.0, 9.0) at visits 1, 5 and 7.

- - Subjective assessment of efficacy on Urinary Incontinence symptoms using the International Consultation on Incontinence Questionnaire (ICIQ) and Questionnaire for Female Urinary Incontinence (QUID) (Appendix 7.0) at visits 1, 5 and 7.
- - Subjective assessment of quality of life change using Pelvic Floor Impact Questionnaire (PFIQ-7) (Appendix 8.0) at visits 1, 5 and 7.
- - Subjective assessment of improvement of pelvic organ prolapse, colorectal-anal disease or urinary distress as measured by the Pelvic Floor Distress Inventory Questionnaire (PFDI-20) (Appendix 10.0) at visits 1, 5, 7.

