length and diameter, measurement of the introitus, and length of the labia majora and minora. Measurements will be obtained following POP-Q protocol

- Time required: 15 minutes

**Visit 7:** Midwest Plastic Surgery – Follow-up visit – 8 weeks following second treatment

- Photographs of the treatment area will be taken
- Questionnaires will be completed
- Time required: 45 minutes

- After each treatment and at all visits, adverse events will be recorded.

Duration of each treatment visit is specified.

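### A treated woman who does not return for the second-treatment visit has no scheduled post-treatment questionnaire, so the paired questionnaire results describe only women who returned

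*Protocol*

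**What the plan says.** The protocol's Subjective measurements section gives FSFI, PISQ-12, ICIQ, QUID, PFIQ-7 and PFDI-20 the same schedule. The PFIQ-7 line is typical: "Subjective assessment of quality of life change using Pelvic Floor Impact Questionnaire (PFIQ-7) (Appendix 8.0) at visits 1, 5 and 7".

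Study Duration defines the relevant visits:
- Visit 4: "Antares Institute Follow-up visit – 8 weeks following first treatment". It lists the pelvic floor assessment and no questionnaires.
- Visit 5: "Midwest Plastic Surgery – 2 nd treatment". Questionnaires are completed, but the text does not say whether before or after the procedure.
- Visit 6: "Antares Institute Follow-up visit – 8 weeks following second treatment". This is the final contraction reading.
- Visit 7: "Midwest Plastic Surgery – Follow-up visit – 8 weeks following second treatment". Questionnaires are completed.

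Under Objective measurements, contraction is assessed "before each treatment and at follow up visits (8 weeks after each treatment). Visits 2, 4 and 6".

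Primary Endpoints lists "Voluntary withdrawal of the patient at any time". The available text describes no early-termination contact and no follow-up of a woman who has one treatment only.

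The SAP admits to the performance set any woman with one or more performance measurements after treatment. It uses observed values without imputation and tests change with a paired t-test at two-sided 0.05.

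**The concern.** Whether a woman comes back for a second session may well depend on how the first one felt and whether it helped. If the first post-treatment questionnaire is available only to those who come back, the before-after change in sexual function, urinary, prolapse and colorectal-anal symptoms and quality of life is conditioned on that decision. These questionnaires carry the symptom and quality-of-life secondary objectives. With a single arm, there is no comparison group in which the same selection would show itself.

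This differs from the usual complaint about analysing completers. For contraction, a woman who stops after Visit 4 still leaves an interim value that an analysis can use. For the questionnaires she leaves only a baseline. A sensitivity analysis could bound what is missing, but only a change in collection would supply it.

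**Working it through.** **Step 1: which assessments depend on returning.** From the protocol's Subjective measurements, Objective measurements and Study Duration sections:

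| Measure | Post-treatment visits | Depend on returning for the second treatment | Left for a woman seen at Visit 4 but not at Visit 5 |
|---|---|---|---|
| Six questionnaires | 5, 7 | 2 of 2 | 0 |
| Contraction | 4, 6 | 1 of 2 | 1 (Visit 4) |

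Her Visit 4 reading would appear to place her in the SAP's performance set. She has no post-treatment questionnaire to pair with Visit 1, so she contributes nothing to those t-tests.

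**Step 2: inputs for size.** From the documents: at least 20 women, one arm, paired t-test, two-sided 0.05 (2.5% in the direction of benefit). There is no planned figure to reproduce, because no drop-out rate, effect size or SD is stated. Assumed: 2, 4 or 6 of 20 stop (10%, 20%, 30%).

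**Step 3: stoppers with zero change.** If a share p stops and has no change, the returners' mean exceeds the all-treated mean by the factor 1/(1 - p): 1/0.9 = 1.11, 1/0.8 = 1.25, 1/0.7 = 1.43. That is an overstatement of 11%, 25% or 43%.

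**Step 4: false benefit by simulation.** Each trial has 20 women whose change scores have mean 0 and SD 1. Willingness to return has correlation r with change. The 2, 4 or 6 least willing are removed and the paired t-test is run on the remaining 18, 16 or 14. At r = 0.5 the mean false gain is 0.093, 0.167 and 0.236 SD. The gain is proportional to r, so at r = 0.3 it is 0.3/0.5 = 0.6 times as large: 0.056, 0.100 and 0.142 SD.

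| Stop | r = 0.3 | r = 0.5 |
|---|---|---|
| 2 of 20 | about 4% | about 6% |
| 4 of 20 | about 6% | about 10% |
| 6 of 20 | about 8% | about 15% |

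The entries are the chance of a significant apparent improvement, nominally 2.5%. Repeat runs agree to within about half a percentage point.

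**Step 5: cross-check with a simpler model.** Let stoppers do worse than returners by D = 0.5 to 1.0 SD, with an all-treated mean change of zero. The returners' mean is then shifted by (share stopping) x D: 0.05-0.10, 0.10-0.20 and 0.15-0.30 SD. The noncentral t distribution with 18, 16 and 14 women gives 3.9-5.9%, 5.7-11.3% and 7.5-17.9%. The order of magnitude is the same.

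**The case against.** Several points on the other side have force.

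- **Follow-up wording.** The opening sentence of Study Duration counts follow-up from the last treatment, not the second. For a woman treated once, that could mean 8 weeks after the first. This stands as an inconsistency with the Visit 6 and 7 entries, and the passages must be reconciled. It does not close the gap, because the visit entries that carry the questionnaires still depend on the second treatment.
- **Attendance, not treatment.** A woman could attend Visit 5, complete the forms and then decline treatment, leaving one post-treatment outcome. True. The point is therefore about not returning for Visit 5. The protocol does not provide for this case or state the order within the visit.
- **Analysis could help.** Carrying baseline forward or a tipping-point analysis would bound the bias. True, but neither is planned, and a bound is not an observation.
- **Assumed size and direction.** Inclusion requires willingness to keep to the schedule, and there are only two sessions, so 30% stopping may be pessimistic. A woman might also skip the second session because she is content, which would reverse the bias. Both stand, and the low-end figures deserve equal weight.
- **Primary objective.** Contraction is largely spared by Visit 4. Agreed.

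**Conclusion.** The point holds as a weakness of the data-collection schedule that should be corrected. Both post-treatment questionnaire visits depend on returning for the second-treatment visit, so the paired questionnaire analyses include only women who returned. For contraction, only the final reading at Visit 6 is affected.

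The size is illustrative. With 10-30% stopping, the 2.5% chance of a false benefit becomes about 4-8% at correlation 0.3 or 6-15% at correlation 0.5. It rests on an assumed drop-out rate and on poor responders being the ones who stop; if satisfied women stop, the planned analysis would understate the benefit.

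A reader might infer three stronger things that the documents do not support:
- That the plan treats stopping the device as leaving the study. It says only that withdrawal is possible at any time, and is silent on women who stop treatment but would still answer questions.
- That the satisfaction assessment certainly misses these women. The objective reads "Evaluate patients' satisfaction at follow up visit", without an instrument or visit number, and Visit 4 is itself called a follow-up visit.
- That the bias necessarily favours the device. The direction depends on why women stop, which the schedule as written would not reveal.

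**What to change.** 1. Collect the week-8 questionnaires from every treated woman. Those who attend Visit 5 complete them before any treatment that day. Those not returning complete them at Visit 4, if this is known by then, or by post. Record the mode of completion.
2. Leave Visits 6 and 7 at 8 weeks after the second treatment for women who have it; dating them from the first treatment for everyone could break that interval if the second session slips. For women who do not have it, carry out the same assessments about 16 weeks after the first treatment (8 + 8 weeks). Reconcile the two descriptions of follow-up in Study Duration, one counted from the last treatment and the other from the second.
3. State that not having the second treatment does not end data collection, and that only withdrawal of consent does.
4. Report how many treated women have, and do not have, post-treatment questionnaires.

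This takes a short amendment, with no new instrument or staff. The costs are a few posted forms, extra assessments for women who stop, and more time at Visit 4 if forms are completed there, since it is allotted 15 minutes. Completion mode will differ partly by whether a woman stopped, which is why it should be recorded. Some women will still refuse, and the reported gains may be smaller.
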